10. STATISTICAL METHODS

This will be a Level 1 study (RCT).

10.1 Hypothesis

Intervertebral discs and adjacent spinal muscle tissue of the lumbar spine will show a change in the apparent diffusion coefficient and perfusion coefficient on MRI after an SMT intervention.

10.2 Determination of Sample Size

N = 70 (25 per patient group, 20 controls). Rationale: Based on the study results by Wong et al.¹⁸, we expect an increase in ADC values of at least 6.5% (CI: 3.88%-9.13%) in receivers of SMT-intervention compared to no change in the control-intervention group. 25 patients per group will provide a power of 0.8 (1-beta) to detect an effect of 0.9 at an alpha-level of 0.05⁴⁸. Additionally, the repeatability of IVIM-MRI on musculoskeletal tissue will be assessed in 20 control subjects.

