10.3.2 Primary Analysis

Our hypothesis is that a spinal segment receiving an SMT-intervention will show a change in the diffusion and pseudodiffusion coefficient that is significantly higher than a spinal segment receiving a control intervention. Distributions of the ADC and perfusion coefficient obtained before and after intervention will be tested for the assumptions of normality using the Shapiro-Wilk test. In case of non-normality, data transformation will be used to normalize data. Should this not be possible, non-parametric tests will be used. Two separate repeated measures analysis of variance (ANOVA) will be used to test for effects of time (pre- vs. post-intervention) on ADC and perfusion coefficient with intervention (experimental vs. control intervention) and group (degenerated vs. non-degenerated painful segments) as the between-subject variables.

The PI will supervise the primary analysis as described above. It will be analyzed using SPSS (version 23) at the end of the recruitment period and after obtaining all necessary data.

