10.4 Handling of missing data and drop-outs

Intention to treat analysis is planned to account for missing data.

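### Section 10.2 presents the central estimate of the ADC increase (6.5%) as a minimum, and its power of 0.8 does not follow from the inputs given (0.88 on the plain reading)

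*Combined protocol and SAP*

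**What the plan says.** Section 10.2 (Determination of Sample Size) sets the size as "N = 70 (25 per patient group, 20 controls"). The 20 controls are there for repeatability and lie outside the randomized comparison. The expected effect is given as "we expect an increase in ADC values of at least 6.5% (CI: 3.88%-9.13%) in receivers of SMT-intervention", "compared to no change in the control-intervention group". The section then says that "25 patients per group will provide a power of 0.8 (1-beta") for an effect of 0.9 at alpha 0.05.

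It does not give an SD, the type of effect size, the sidedness, the test, the confidence level of the interval or a dropout allowance. It does not say how 0.9 was obtained or that 0.9 is the 6.5% in standardized form. The synopsis repeats the numbers of participants and refers to existing data, but adds no other effect. No section gives power at a smaller effect.

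Section 10.3.2 (Primary Analysis) words the hypothesis as a change "that is significantly higher than a spinal segment receiving a control intervention" and plans that "Two separate repeated measures analysis of variance (ANOVA) will be used to test for effects of time", with intervention and degeneration as between-subject factors and non-parametric tests as a fallback. On missing data, Section 10.4 says only "Intention to treat analysis is planned to account for missing data".

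**The concern.** The sentence contradicts itself. A value described as the least to be expected should sit at or near the bottom of its own interval, but this one sits in the middle, and half of the printed range lies below it. Because 6.5% is the only ADC effect offered in support of N, the label makes the design look safe for every effect in that range.

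The power figure beside it should be a short calculation from the printed inputs, and it does not come out. A reader therefore cannot tell which basis was used, or what power the trial has at 6.5% or at anything smaller. That matters most for a non-significant result, which would be read against a claim of 80% power for a supposed minimum effect. Section 10.3.2 promises tests but no between-arm estimate with a confidence interval to guide that reading.

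**Working it through.** **1. Position of 6.5% in its interval.** Both limits are from Section 10.2. Midpoint = (3.88 + 9.13)/2 = 6.505. Half-width = (9.13 − 3.88)/2 = 2.625. So 6.5% is the centre.

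**2. The plan's own power figure.** From Section 10.2: effect 0.9, n = 25 per arm, alpha 0.05. Assumed: 0.9 is a standardized mean difference d, and the test is two-sided. With two time points, comparing change between two arms amounts to a two-sample t-test on change scores (the degeneration factor is ignored here).

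- Noncentrality = d × √(n/2) = 0.9 × √12.5 = 3.182, with df = 48 and critical t = 2.011.
- Power by the exact noncentral t = 0.877. By normal approximation, Φ(3.182 − 1.960) = Φ(1.222) = 0.889.
- Stated: 0.8. It does not reproduce.
- n per arm for 0.80 at d = 0.9: 20 gives 0.792 and 21 gives 0.812.

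**3. Possible explanations of the gap.** Section 10.2 states none of them.

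| Reading | Power at d = 0.9 |
|---|---|
| One-sided 0.05, t, 25 per arm | 0.932 |
| Wilcoxon-Mann-Whitney, minimum efficiency 0.864 | 0.823 |
| Wilcoxon-Mann-Whitney, efficiency 3/π | 0.861 |
| Two-sided alpha 0.025, t, 25 per arm | 0.804 |
| 21 evaluable per arm (16% loss: 1 − 21/25) | 0.812 |

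Two come close: an alpha halved across the two ANOVAs, and 21 per arm inflated to 25 for dropout. But the section says 0.05 and gives no dropout rate.

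**4. Power below 6.5%.** Further assumptions, not in the plan: 0.9 = 6.5%/SD, and the SD is the same at every effect. Then SD = 6.5/0.9 = 7.22 percentage points.

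| True increase | d = increase/7.22 | Power (two-sided t, 25 per arm) |
|---|---|---|
| 6.5% | 0.900 | 0.88 |
| 5% | 0.692 | 0.67 |
| 3.88% | 0.537 | 0.46 |

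If the stated 0.80 at 6.5% is taken as right instead, the d that gives 0.80 with 25 per arm is 0.809. At the lower end d = 0.809 × 3.88/6.5 = 0.483, and power is 0.387.

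**5. Sensitivity at 3.88%.** With d = 0.537, other two-sided readings give 0.476 (normal approximation), 0.407 (Wilcoxon-Mann-Whitney, minimum efficiency), 0.397 (21 evaluable per arm) and 0.348 (alpha 0.025). A one-sided t-test gives 0.59. The range for two-sided readings is therefore about 0.35 to 0.48.

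**The case against.** Powering on a point estimate is ordinary practice, and power is lower at the lower confidence limit of any such estimate. The section prints the whole interval, so the uncertainty is visible, and it ties power to an effect of 0.9, not to a smallest plausible effect. This stands: the low-end power is not a design error in itself. What remains is the wrong label on 6.5% and a power figure that does not follow from its inputs.

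The link between 0.9 and 6.5% is also not in the text. This stands too. The 7.2-point SD and every power value below 6.5% depend on it, and the mismatch between 0.88 and 0.8 suggests that the sponsor may have calculated differently.

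Three stronger readings are tempting, and the documents do not support them.

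- A reader might infer that the plan's 0.8 drops to 0.46. It does not: 0.46 belongs with 0.88, and 0.8 leads to about 0.39.
- A reader might infer that a null result could never exclude 3.88%, and that 3.88% should become the threshold for declaring no effect. The expected 95% CI half-width is 2.011 × 7.22 × √(2/25) = 4.11 points, only just above 3.88, and an SD below about 6.8 (3.88/(2.011 × √(2/25))) reverses the comparison. Nowhere is 3.88% called a relevant difference; it is only an interval limit taken from a cited study.
- A reader might infer that the plan will treat non-significance as absence of effect. No section says so.

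**Conclusion.** Two statements in Section 10.2 are wrong or unsupported as written. The first needs no assumption: 6.5% is the centre of its interval (6.505) and not a minimum. The second needs only the plain reading of 0.9 as a standardized difference and a two-sided test: power is 0.88, not 0.8, and no allowance, alpha split or non-parametric basis is stated for the calculation. On that reading the printed power is too low, so the mismatch does not show that the randomized groups are too small for an effect of 0.9.

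The loss of power towards 3.88% is conditional. It is 0.88 to 0.46 if 0.9 standardizes 6.5% with a fixed SD, and 0.80 to about 0.39 if the stated power is right. Every two-sided reading tried leaves it below one half, but the exact value cannot be settled without the sponsor's SD and test. The point concerns planning statements and is no argument for a larger trial.

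**What to change.** In Section 10.2:

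- Delete 'at least' and describe 6.5% as the best estimate, with the confidence level of its interval.
- State how 0.9 was obtained: the SD used, the test and the sidedness.
- Either correct the power at 0.9 (0.88 on the plain reading) or state the dropout allowance, alpha split or test that makes it 0.80.
- Report power at the lower end of the interval on that same basis.

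In Section 10.3.2, add that the between-arm difference will be reported with its 95% CI. Do not adopt 3.88% as a margin for declaring no effect. Do not enter the back-calculated SD of 7.2 points, or the difference of about 5.8% detectable with 80% power that follows from it (0.809 × 7.22 = 5.84), as planning facts unless the sponsor confirms the SD.

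The cost is a few sentences and a less favourable power figure at the low end. N, procedures and planned tests stay as they are.

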10.3 Planned Analyses

Distributions of the ADC and perfusion coefficient obtained at the two time points (before and after intervention) will be tested for the assumptions of normality using the Shapiro-Wilk test. In case of non-normality, data transformation will be used to normalize data. Should this not be possible, non-parametric tests will be used. Two separate repeated measures analysis of variance (ANOVA) will be used to test for effects of time (pre- vs. post-intervention) on ADC and perfusion coefficients with intervention (experimental vs. control intervention) and group (degenerated vs. non-degenerated painful segments) as between-subject variables.

We will estimate the repeatability of IVIM-MRI in measuring perfusion in musculoskeletal tissue using paired t-tests and the intraclass correlation coefficient ICC⁴⁹.

10.3.1 Dataset to be Analysed, analysis populations

The statistician will supervise the analysis as described in 11.4.

10.3.2 Primary Analysis

Our hypothesis is that a spinal segment receiving an SMT-intervention will show a change in the diffusion and pseudodiffusion coefficient that is significantly higher than a spinal segment receiving a control intervention. Distributions of the ADC and perfusion coefficient obtained before and after intervention will be tested for the assumptions of normality using the Shapiro-Wilk test. In case of non-normality, data transformation will be used to normalize data. Should this not be possible, non-parametric tests will be used. Two separate repeated measures analysis of variance (ANOVA) will be used to test for effects of time (pre- vs. post-intervention) on ADC and perfusion coefficient with intervention (experimental vs. control intervention) and group (degenerated vs. non-degenerated painful segments) as the between-subject variables.

The PI will supervise the primary analysis as described above. It will be analyzed using SPSS (version 23) at the end of the recruitment period and after obtaining all necessary data.

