
Study Schedule:
	
September 2018: Application for ethical approval December 2018: Inclusion of first participant December 2019: Inclusion of last participant June 2020: Statistical analysis, Report

Investigator(s):
	
Dr. med. chiro. [name], Universitätsklinik Balgrist, [name], [contact] [contact]
 
M. chiro. med. [name], Universitätsklinik Balgrist, [name], [contact] [contact]
 
PD Dr. med. [name], Universitätsklinik Balgrist, [name], [contact]
 
PD Dr. med. [name], Universitätsklinik Balgrist, [name], [contact]
 
[name], PhD, University Hospital Zurich Center of Experimental Rheumatology, Balgrist Campus, [name]
 
PD [name], Balgrist Campus, [name]
 
[name]. med. [name], Universitätsklinik Balgrist, [name], [contact]

Study Centre(s):	University Hospital Balgrist [name] [name] and Balgrist Campus [name] [name]
Statistical Considerations:	Parametric and non-parametric statistical tests will be performed as appropriate. After an analysis of existing data ^{17,18} , 50 patients and 20 controls are expected to be included in this study within a recruiting period of 12 months.
GCP Statement:	This study will be conducted in compliance with the protocol, the current version of the Declaration of Helsinki, the ICH-GCP or ISO EN 14155 (as far as applicable) as well as all national legal and regulatory requirements.

Abbreviations

AE	Adverse Event
ADC	Apparent Diffusion Coefficient
ASR	Annual Safety Report
BASEC	Business Administration System for Ethical Committees
CA	Competent Authority (e.g. Swissethics)
CEC	Competent Ethics Committee
CRF	Case Report Form
ClinO	Ordinance on Clinical Trials in Human Research (in German: KlinV, in French: OClin)
eCRF	Electronic Case Report Form
CT	Computed tomography
CTCAE	Common terminology criteria for adverse events
DWI	Diffusion-weighted imaging
EP	End plate
FSE	Fast Spin Echo
GCP	Good Clinical Practice
HRA	Federal Act on Research involving Human Beings
HVLA	High-velocity, low-amplitude
ISO	International Organisation for Standardisation
IVIM	Intravoxel incoherent motion
MD	Medical Device
MRI	Magnetic resonance imaging
ODI	Oswestry Disability Index
PI	Principal Investigator
SMT	Spinal Manipulative Therapy
SOP	Standard Operating Procedure

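### A Shapiro-Wilk test on the raw before and after values decides how the primary data are analysed; it checks the wrong distribution and leaves the effect scale to the data

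*Combined protocol and SAP*

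**What the plan says.** Section 10.3 introduces the check: "Distributions of the ADC and perfusion coefficient obtained at the two time points (before and after intervention) will be tested for the assumptions of normality". Section 10.3.2 repeats it for the primary analysis: "Distributions of the ADC and perfusion coefficient obtained before and after intervention will be tested for the assumptions of normality using the Shapiro-Wilk test". The consequence follows at once: "In case of non-normality, data transformation will be used to normalize data. Should this not be possible, non-parametric tests will be used". The model behind this check is "Two separate repeated measures analysis of variance (ANOVA) will be used to test for effects of time (pre- vs. post-intervention) on ADC and perfusion coefficient"; treatment arm and degeneration status enter as between-subject factors. The hypothesis in 10.3.2 is that the change is larger after SMT than after the control intervention.

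No transformation, non-parametric test or significance level for the check is named. The plan does not say whether a rejection at one time point, or for one parameter or tissue, switches the others. The synopsis is equally open: "Parametric and non-parametric statistical tests will be performed as appropriate". Residuals and change scores are not checked anywhere.

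On scale, the synopsis writes the outcome as a delta. Section 10.2 plans ADC as a percentage, "we expect an increase in ADC values of at least 6.5" per cent against no change in the control arm, and also gives a standardised effect of 0.9. No section says whether the analysed effect is absolute or relative.

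**The concern.** This is a stated decision rule applied to the wrong quantity, not merely missing detail. With two time points, the comparison of arms uses each patient's change. Stable differences between patients, including those between degenerated and non-degenerated segments, cancel from the change but remain in the raw values. A skewed or mixed spread of baseline ADC can trip the rule when the model is sound. An awkward distribution of change can pass unseen when the raw values look normal.

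The rule also settles what is reported. An untransformed analysis gives an absolute difference, a log transformation gives a ratio, and a rank test gives neither. Simple two-sample or paired rank tests also have no place for the planned degeneration factor. Section 5.3 allows unblinding after the last inclusion and 10.3.2 places the analysis after all data are in. Nothing requires the transformation or fallback to be fixed before then.

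**Working it through.** **1. The plan's own figure.** Section 10.2 gives 25 per group, effect 0.9, alpha 0.05 and power 0.80. For a two-sided two-sample t-test, the noncentrality is 0.9 × √(25/2) = 3.18 on 48 degrees of freedom, so power is 0.877. Power 0.80 needs 21 per group. The stated inputs thus give more power than stated. That is a separate matter; 0.877 serves here only as a benchmark.

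**2. Which distribution matters.** For patient *i* in arm *a* with degeneration status *g*:

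- pre = μ + γg + s + e₁
- post = μ + γg + s + τ + δa + e₂
- change = τ + δa + (e₂ − e₁)

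The patient effect *s* and the stable degeneration difference γ drop out of the change. If the response also differs by *g*, that term enters the model for change as a factor. The test of δ needs approximately normal (e₂ − e₁), whatever the shape of *s* and γg.

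**3. How often the raw check fires.** Assumptions: 50 patients, exactly normal residuals, pre/post correlation 0.7 to 0.9, Shapiro-Wilk at 0.05, one outcome tested before and after, groups pooled. Two independent 5% tests would give 1 − 0.95² = 9.75%. Simulated rates:

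| Degeneration gap (within-group SD) | At least one raw test rejects | Residual test rejects |
|---|---|---|
| 0 | about 9-10% | about 5% |
| 2 (degenerated share 50-85%) | 10-27% | about 5% |
| 3 (degenerated share 50-85%) | 47-74% | about 5% |

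The lower ends at 2 and 3 SD belong to a 50% share. The upper ends move by a few points with how the share is generated.

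**4. Other shapes.** With normal change scores and a log-normal baseline (log-SD 0.1, 0.2, 0.3, 0.4, 0.5), at least one raw test rejects in 15%, 36%, 60%, 82% and 93% of trials, while a test on change rejects in about 5%. In the opposite case, normal baseline values and change following a t distribution with 2 degrees of freedom, the raw tests flag 15% and the test on change 86%.

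**5. Scale.** A 6.5% rise on baseline *b* is 0.065*b*, so the absolute effect varies with *b* and the ratio does not. Assume a true +6.5% and an SD of change of 6.5/0.9 = 7.2%, with 25 per arm:

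| Baseline CV | Raw check fires | Power, raw difference | Power, log ratio | Raw and log disagree on significance |
|---|---|---|---|---|
| 10% | 22% | 0.84 | 0.85 | 2% |
| 20% | 42% | 0.83 | 0.85 | 5% |
| 30% | 65% | 0.82 | 0.86 | 7% |
| 50% | 92% | 0.77 | 0.85 | 12% |
| 100% | almost 100% | 0.59 | 0.85 | 30% |

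These data were generated with a multiplicative effect, which favours the log scale by construction. The documents give no CV.

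**6. Type I error.** With no arm difference, choosing raw or log by the Shapiro-Wilk result gave 0.047 to 0.054.

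**7. Power of possible fallbacks.** Take effect 0.9 in SDs of change and correlation 0.7. The SD of change is √(2 × (1 − 0.7)) = 0.775 raw SDs, so the shift is 0.9 × 0.775 = 0.697 raw SDs.

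- Post values only, Mann-Whitney (standardised effect 0.697): about 0.64, or about 0.41 with a 2 SD degeneration gap.
- Change, Mann-Whitney: about 0.86.
- Change, t-test: about 0.885 simulated, close to the 0.877 in step 1.
- Post value adjusted for baseline (0.697/√(1 − 0.7²) = 0.976): about 0.91.

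**The case against.** Several counter-arguments stand, and they limit the point.

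- **False positives.** A reader might infer that letting a pre-test choose the scale inflates type I error. Step 6 does not show this for a raw-versus-log choice. Unnamed transformations and tests leave more freedom than was simulated, but no inflation has been demonstrated.
- **Higher trigger rates.** Counting both outcomes together gives at least one rejection in about 1 − 0.95⁴ = 18.5% of trials with no gap, and as much as 80% at 3 SD. The plan specifies two separate ANOVAs and does not say that a rejection for perfusion switches ADC, so the rates here are per outcome. At a 2 SD gap and a 50% share, the rate is no higher than with no gap.
- **Pooling.** The plan does not say that values are pooled over degeneration groups. If each cell were checked separately, the mixture argument would go. The skewed-baseline argument and the multiple tests would remain, though smaller cells reject less often.
- **The fallback.** A reader might expect separate within-arm Wilcoxon tests, where reading a significant SMT arm and a non-significant control arm as an effect gave 12-22% false positives under a shared shift of 0.2 to 0.5 SD. The hypothesis in 10.3.2 compares arms on change, so the fallback that fits it is a between-arm test on change. That costs only 0.885 − 0.86 = 0.025 in power. How often any fallback would be reached is unknown.
- **Percentage against absolute.** Section 10.2 also gives a standardised 0.9, and its percentage concerns ADC only. The documents leave the scale open; they do not contradict themselves on it.

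**Conclusion.** The point holds. Sections 10.3 and 10.3.2 make a test on raw values the switch for the primary analysis, although the time-by-intervention test depends on residuals. The mechanism needs no assumption about the data; the rates in step 3 do. Degeneration gaps, shares, correlations and baseline spread are all assumed, because the documents give none.

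The harm is moderate: needless switching, an effect scale not fixed in advance, and possible power loss (about 0.64 against 0.86) if an unnamed fallback used post values only. A reader might also infer that the log scale is required. The documents do not support that: they give no distribution for ADC or the perfusion parameters, and the simulations in step 3 have normal residuals on the raw scale. The log scale is an option with a trade-off.

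**What to change.** In 10.3 and 10.3.2:

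1. Delete the Shapiro-Wilk test on raw values as a decision rule, together with the two branches that follow from it, and align the synopsis sentence on tests.
2. State one primary scale per outcome before unblinding. For ADC, the log scale reported as a percentage is one option, since 10.2 plans a 6.5% change. For perfusion, 10.2 gives no planning effect, so the scale needs its own statement.
3. Analyse the post value by arm with baseline value and degeneration group as covariates. The gain from about 0.885 to 0.91 comes from baseline adjustment and is not evidence about the pre-test.
4. Check residuals descriptively, without letting the result change the primary analysis.
5. Name one between-arm sensitivity test on the change score, stratified by degeneration, for example a stratified permutation test.

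The cost is analysis wording only: no extra patients, scans or visits. If the log scale is chosen, the effect is a ratio and must be back-transformed for readers who want absolute units.

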Measurements and procedures:	
45 minutes prior to the first round of imaging, patients and controls provide baseline information on current pain and function (painDetect questionnaire²⁴, Oswestry Disability Index (ODI)²⁵). Additional information is collected on the localization of pain (pain drawing), whether back or leg pain is dominant, and whether there is a preference in movements or activities (e.g. walking, sitting for a long time, rising from sitting, forward bending or standing)^{26,27-29}.
 
Patients and controls then undergo a clinical examination including assessment of blood pressure and pulse, lower extremity neurological examination³⁰, nerve tension tests, active range of motion of the lumbar spine, facet joint provocation test^{31,32}, and palpatory segmental examination of the lumbar spine^{33,34}. In patients, the skin above the interspinous ligament causing the most pain upon palpation by the examiner is marked with pen. A blood sample of approximately 10-15 ml is obtained from participants agreeing to additionally undergo venipuncture by a medical professional trained in venipuncture. This procedure is not mandatory and is agreed to separately in the informed consent form. The examination is followed by a rest period of 10 minutes.
 
Patients and controls are then evaluated in the MRI-Scanner lying supine. Upon completion of this scan, patients will be randomized either to receive either a total of two spinal manipulative interventions, first in right, then left side-lying position at the segment of the marked interspinous ligament, or receive only pre-SMT positioning by the chiropractor administering the intervention, who places his/her hand on the site of the marked skin above the interspinous ligament without applying pressure, preload or thrust in right and left side-lying position.
 
For patients, three sequential post intervention MRIs are performed immediately after the intervention. Once imaging is complete, the patients exit the scan room and provide post-intervention information on current pain-intensity. Blood pressure and pulse are reassessed. Patients will be contacted after 1 week, 1 month and 3 months and follow-up data will be collected on pain and disability.
 
Controls are reassessed in a second MRI after 20 minutes of supine lying to assess the repeatability of IVIM imaging, and will undergo a third imaging sequence approximately 10 hours later (after partaking in activities of daily life as normal, but excluding strenuous physical activity) in order to assess diurnal changes in perfusion and diffusion parameters on IVIM and DWI imaging. This scan will serve as a positive control that diurnal changes in diffusion parameters described in the nucleus pulposus can be detected³⁵.

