4. STUDY OUTCOMES

4.1 Primary Outcome

Changes in diffusion in intra- and extracellular compartments (D), apparent diffusion coefficient (ADC), perfusion in capillaries (D^*) and volume fraction of capillary perfusion (f) in the intervertebral disc and adjacent spinal muscle tissue in patients before and after an SMT- or control intervention and in controls before and after 20 minutes of lying supine.

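### Adjusting the primary SMT-versus-control test for the baseline MRI value would be a nearly free gain in precision, of a size that depends on an unstated pre-post correlation

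*Combined protocol and SAP*

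**What the plan says.** Section 10.3.2 sets out the primary model: "Two separate repeated measures analysis of variance (ANOVA) will be used to test for effects of time (pre- vs. post-intervention"). It completes the model "with intervention (experimental vs. control intervention) and group (degenerated vs. non-degenerated painful segments) as the between-subject variables". Section 10.3 describes the data as "obtained at the two time points (before and after intervention"), so time has two levels. The baseline value enters only as the first of two responses. Neither section uses it as a covariate or plans a baseline-adjusted sensitivity analysis.

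The hypothesis in 10.3.2 is a between-arm comparison of change: the treated segment "will show a change in the diffusion and pseudodiffusion coefficient that is significantly higher than a spinal segment receiving a control intervention". Section 4.1 likewise defines the primary outcome as change "in patients before and after an SMT- or control intervention". The analysis text names effects of time. It does not name the time-by-intervention term, which is the term that matches this hypothesis.

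The design is "N = 70 (25 per patient group, 20 controls"). The Synopsis and sections 5.1 and 8.3.2 place randomisation after the first scan. For patients, the Synopsis says that "three sequential post intervention MRIs are performed immediately after the intervention", and section 5.1 agrees on three. Section 8.3.2 describes a single second round of imaging, and the analysis text does not say which post scan supplies the post value.

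**The concern.** With two time levels, the time-by-intervention F-test in a repeated-measures ANOVA is the test on post minus pre. This fixes the coefficient of the baseline value at 1. In a randomised comparison the arms differ at baseline only by chance, and with equal SDs the best coefficient is the pre-post correlation r. If r is below 1, subtracting the whole baseline over-corrects: an arm that happens to start high will tend to show too small a change. ANCOVA estimates the coefficient from the data.

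At stake is precision with 25 patients per arm. Randomisation is stratified by age and sex in section 5.2.1, with degenerative changes added in section 6.3. It is not stratified by the baseline diffusion or perfusion values, so nothing in the design balances those values directly.

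**Working it through.** **Inputs from the documents.** 25 patients per arm, alpha 0.05, an effect of 0.9 and stated power 0.8 (section 10.2); two time levels (10.3); intervention and degeneration as between-subject factors (10.3.2).

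**Assumptions.** The test is two-sided. The 0.9 is in SDs of change; section 10.2 does not say so. Pre and post SDs are equal. One post value is used per patient. No pre-post correlation, repeatability coefficient or SD is given for any parameter, so r is taken over 0.3 to 0.98.

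**1. The plan's own figure.** The noncentrality is 0.9 × √(25/2) = 3.18. The two-sample t-test then has power 0.877 (0.876 with 46 error degrees of freedom for the four intervention-by-degeneration cells), not 0.80. Power of 0.80 needs about 20 to 21 per arm. Two unstated variants do lead to 25: two-sided alpha 0.025 (n = 24.8, power 0.804), or 21 per arm inflated for 15% dropout (21/0.85 = 24.7). The mismatch is on the conservative side and does not decide this point. The planned test is taken as having power 0.88.

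**2. Variance ratio.** With common SD σ:

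- change score: variance per patient 2σ²(1 − r)
- ANCOVA: residual variance σ²(1 − r²)
- ratio, ANCOVA to change score: (1 − r²) / [2(1 − r)] = (1 + r)/2
- estimating the slope with N = 50 multiplies this by about 1 + 1/46 = 1.022

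Example at r = 0.5: 0.75 × 1.022 = 0.77.

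**3. Power.** The noncentrality becomes 3.18/√(adjusted ratio), with 47 degrees of freedom.

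| r | (1 + r)/2 | With small-sample factor | ANCOVA power | Planned test |
|---|---|---|---|---|
| 0.3 | 0.65 | 0.66 | 0.97 | 0.88 |
| 0.5 | 0.75 | 0.77 | 0.945 | 0.88 |
| 0.8 | 0.90 | 0.92 | 0.90 | 0.88 |
| 0.9 | 0.95 | 0.97 | 0.89 | 0.88 |
| 0.95 | 0.975 | 1.00 | 0.88 | 0.88 |
| 0.98 | 0.99 | 1.01 | 0.87 | 0.88 |

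**4. Simulation.** 20,000 trials per setting, with 50 patients and the degeneration factor in both models, gave variance ratios of 0.67, 0.77, 0.92, 0.97, 1.00 and 1.01 at the same values of r. Type I error was about 5% for both methods. If the true effect is 0.7 SD of change, the planned test has power of about 0.68. ANCOVA then has 0.84, 0.79, 0.69 and 0.68 at r = 0.3, 0.5, 0.9 and 0.95.

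**5. Chance baseline difference.** Under simple randomisation, one standard error of the baseline difference is √(2/25) = 0.28 baseline SD. The change-score estimate shifts by (1 − r) times that difference, in the opposite direction: 0.5 × 0.28 = 0.14 baseline SD at r = 0.5. There the SD of change equals the baseline SD, so this is 0.14/0.9, or about 16% of the planned effect. The stratified blocks and the degeneration factor make such differences smaller to the extent that they relate to the baseline values.

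**The case against.** The planned model is legitimate. It keeps its 5% error rate, is unbiased over randomisations, and on the plan's own inputs has power above the stated 0.80. The outcome and hypothesis are framed as change, so the model answers the question asked. All of this stands. It does not count against adjustment, because regressing either the post value or the change on arm and baseline gives the same arm coefficient. ANCOVA therefore estimates the same between-arm effect.

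The stronger objection is that r is unknown. Both scans belong to one visit, so a high correlation cannot be excluded, and from about 0.95 upward the gain is nil or slightly negative. For ADC, the only parameter in the sample-size rationale, adjustment might bring nothing. This also stands. But a high r cannot be assumed either: patients leave and re-enter the scanner between scans, and the repeatability of IVIM is something the trial sets out to measure.

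Two stronger readings are tempting. A reader might infer that the perfusion parameters are noisier than ADC and so lose most. The documents nowhere say this; the gain is largest for whichever parameters have the lowest pre-post correlation. A reader might also turn the ratio into a known loss, for example 25/0.75 = 33 patients per arm at r = 0.5. That equivalence leaves out the small-sample factor and treats an assumed r as a fact.

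**Conclusion.** This is a free improvement in efficiency. The SMT-versus-control test is a change-score test, and because patients are randomised after baseline, adjusting for the value already collected is at least as precise apart from about 1-2% of variance for estimating the slope.

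The saving is about 34% of variance at r = 0.3, 23% at 0.5, 8% at 0.8 and 3% at 0.9. It vanishes near 0.95 and becomes a loss of about 1% at 0.98. That asymmetry supports adjusting without knowing r. The figures rest on equal pre and post SDs, the 0.9 read as SDs of change, and one post value per patient. Unequal SDs would change the ratios, but ANCOVA would remain at least as precise in large samples. The relevant r is the one within degeneration groups.

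A reader might infer that the planned test is biased or invalid. The documents and the calculations do not support that.

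**What to change.** In sections 10.3 and 10.3.2, make the primary SMT-versus-control test an ANCOVA for each parameter:

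- outcome: the post-intervention value, stating which of the three post-intervention scans supplies it;
- terms: arm, the patient's own baseline value of that parameter, and the planned degeneration factor;
- tested term: the arm effect, named as such;
- report: the adjusted SMT-minus-control difference with its 95% confidence interval.

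The comparison of degenerated with non-degenerated segments is not randomised, so show the unadjusted change there as well.

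The cost is a sentence or two in the analysis section and one degree of freedom, with no new data. The downside is a variance loss of about 1% if r is about 0.98.
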